1. PROTOCOL SYNOPSIS FOR STUDY OTX203158

Rationale

This study will assess and compare the molecular immune profile of cells derived from the inguinal lymph nodes (iLN) in healthy volunteers (HVs) and New Onset Type 1 Diabetes Mellitus (NOT1D) subjects, to better understand the immunological processes that may lead to beta cell destruction. It is hypothesised that early changes in the immune system in NOT1D subjects can be detected in immune cells from the iLNs that will be distinct from changes observed in peripheral blood derived immune cells, such as for example Peripheral Blood Mononuclear Cells (PBMCs). Novel biomarkers of disease activity may be identified, potentially supporting the early readout of therapeutic efficacy in future Type 1 Diabetes (T1D) trials.

Objective(s)/Endpoint(s)

Objectives	Endpoints
Primary	
1) To assess the frequency and phenotype of leukocyte subsets in iLN and peripheral blood in HVs and NOT1D subjects	
 Absolute number and/or proportion of leukocyte subsets in iLN and peripheral blood
Secondary	
1) To assess the frequency and phenotype of leukocyte subsets in iLN core biopsies and iLN fine needle aspirates in HVs and NOT1D subjects	
 Absolute number and/or proportion of leukocyte subsets in iLN core biopsies and iLN fine needle aspirates.
2) To assess the safety and tolerability of iLN biopsy as well as expectations and experience of the biopsy procedure.	
 Number of AEs and SAEs following lymph node biopsy procedure Descriptive data obtained by a questionnaire on the acceptability of iLN biopsy in research setting.
Exploratory*	
1) To assess suppression activity of T regulatory lymphocytes from the iLN and peripheral blood in HVs and NOT1D subjects	
 Relative levels of T lymphocyte suppressive activity of cells from iLN and peripheral blood respectively
2) To assess the frequency of cytokine-producing lymphocytes in HVs and	
 Proportion of lymphocyte populations producing pro-inflammatory and/or anti-

Objectives	Endpoints
NOT1D subjects	inflammatory cytokines in iLN and peripheral blood
3) To assess clonal expansion of T and B lymphocyte populations in HVs and NOT1D subjects	
 Comparison of TCR and BCR usage in lymphocytes in iLN and peripheral blood
4) To assess the gene expression fingerprint of auto-antigen specific lymphocytes in HVs and NOT1D subjects	
 Gene expression levels of sorted auto antigen stimulated T lymphocyte populations in iLN and peripheral blood
5) To assess the phenotype and transcriptomic fingerprint of stromal cells from iLN core biopsy samples in HVs and NOT1D subjects	
 Absolute number and/or proportion of stromal cell subsets and gene expression levels of stromal cell subsets from iLN core biopsy samples

* The Exploratory endpoints are listed in order of priority and the conduct of any experimental assays will be dependent on the material available (i.e. number of cells obtained) from iLN biopsies and peripheral blood.

Overall Design

T1D

Diagnosis

(N.B. "T1D diagnosis" is not applicable to healthy volunteers)

- A multi-centre, non-drug treatment study to compare differences in immune cells derived from iLN and peripheral blood of NOT1D subjects and HVs.
- After informed consent, each subject will attend a screening visit followed by a study visit for iLN biopsy and peripheral blood collection (Day 1). Follow up phone calls after the study visit will be carried out at approximately Day 2-4 and Day 7 to 14. The total duration of this study will be up to 10 weeks, including the screening period.
- A data look will be carried out after the recruitment of a cohort of up to 5 HVs to determine if the quality and quantity of cells derived from either fine needle aspirate or core biopsy of the inguinal lymph node and from peripheral blood are likely to be sufficient to continue the study to meet its primary objective. Full details on this

feasibility analysis will be provided in the Study Reference Manual (SRM) and Reporting and Analysis Plan (RAP).

- An interim analysis will be carried out after the recruitment of 5 evaluable HVs and 5 evaluable NOT1D subjects. The primary purpose of this interim analysis will be to facilitate decision making and study design for a potential follow-up interventional study.

Type and Number of Subjects

Up to 15 evaluable NOT1D subjects and up to 15 evaluable HVs will be enrolled. If subjects prematurely discontinue the study, additional replacement subjects (up to 5 subjects) may be enrolled at the discretion of the sponsor in consultation with the investigator. Evaluable subjects are defined as subjects that provide both iLN biopsy (at least sufficient amounts of cells by one of the two biopsy methods employed to enable the conduct of assays related to at least the primary endpoint) AND at least sufficient amounts of peripheral blood to enable the conduct of assays related to at least the primary endpoint).

Analysis

Descriptive statistics will be calculated for each of the primary flow cytometry cell types by group and sample type (blood / biopsy). Generalized linear models with appropriate link functions will be used to analyze data separately for each flow cytometry cell type to provide estimates for comparisons.

2. INTRODUCTION

Lymph nodes (LNs) are important sites in the body where either an immune response to pathogenic antigens or tolerance is initiated [Sainte-Marie, 2010]. In T1D there is a break down in tolerance against self antigens resulting in immune attack of the beta cells of the pancreas.

In the non-obese mouse model of T1D (NOD mouse) islet specific T-cells can be detected in the pancreatic LN before the onset of disease [Höglund, 1999] and removal of these LNs rescues NOD mice from developing T1D [Gagnerault, 2002]. In addition, in subjects with T1D, auto-reactive T cells isolated from the blood are capable of destroying islet cells when co-cultured *in vitro*, suggesting that immune activation is not only occurring at the pancreas but also in other lymphoid tissues [Unger, 2012]. However, identification of clonal signatures unique to T1D subjects has proven to be difficult due to the low frequency of antigen specific cells in the blood of these subjects. To date, researchers have studied pathogenic T cells in response to insulin-specific antigens in the peripheral blood but the results have shown no significant differences between HVs and T1D subjects [Herold, 2009], most likely due to lack of response to antigen by low affinity T-cell Receptors (TCRs). In addition, emerging data suggest that post-translational modification of insulin-related antigens is playing a role in break of tolerance and destruction of beta cells [van Lummel, 2014].

2.1. Study Rationale

This study will assess and compare the molecular immune profile of cells derived from LNs in HVs and NOT1D subjects, to better understand the processes that may lead to beta cell destruction. Since retrieving peri-pancreatic LN cells is not feasible in a research setting and immune cells circulate quickly throughout the body, we will address our questions using cells from the LNs in the inguinal region. This method has been utilised in subjects with rheumatoid arthritis, subjects at risk of rheumatoid arthritis and HVs [van Baarsen, 2013].

It is hypothesised that early changes in the immune system in subjects with NOT1D can be detected in LNs that will be distinct from changes observed in cells derived from peripheral blood, such as PBMCs. As a result, novel biomarkers of disease activity may be identified, potentially supporting the early readout of therapeutic efficacy in future T1D trials.

2.2. Brief Background

2.2.1. Type 1 Diabetes Mellitus

T1D represents 5-10% of all subjects with Diabetes Mellitus [Maahs, 2010] and is primarily a result of the T cell-mediated destruction of beta cells in the pancreas [Atkinson, 2014]. The disease occurs most often in children, adolescents, and young adults, but can present at any age. T1D has strong Human leukocyte antigen (HLA) associations, particularly with linkage to DR and DQ genes. Autoreactive antibodies precede the onset of disease and have been used for risk stratification in susceptible

subjects [Wasserfall, 2006], however, they cannot predict disease progression. Due to the varying length of time between autoantibody seroconversion and clinical symptoms in subjects, it is postulated that the environment also plays a role in the development of the disease. Environmental factors such as viruses [Yeung, 2011], lack of vitamin D [Hyppönen, 2001], weaning and improved hygiene [Knip, 2010] have all been implicated as triggers for T1D, but their roles remain controversial. Major steps to address this are being undertaken through the longitudinal ‘TEDDY’ study (The environmental determinants of diabetes in the young), which is monitoring genetically susceptible children from birth (<https://teddy.epi.usf.edu/>).

During the preclinical period between seroconversion and disease onset there is progressive loss of beta cells in the pancreatic islets, which impairs the ability of an individual to maintain blood glucose levels within a physiologic range [Rowe, 2011]. A complex interplay between the innate and adaptive arms of the immune system, in response to islet-specific antigens, is responsible for the pathogenesis of T1D. The precise events that trigger the development of an autoimmune attack on and destruction of the beta cells are unclear, but may be driven primarily by cytotoxic T cells. Indeed, islet-derived CD8+ T cells expressed T-cell receptors bound to MHC class 1 tetramers with the beta-cell autoantigen Islet-specific glucose-6-phosphatase catalytic subunit-related protein (IGRP) and other target peptides in NOT1D subjects [Skowera, 2015]. In addition, autoreactive CD8+ and CD4+ T lymphocytes can be detected in peripheral circulation and are directed to many of the same epitopes in recent-onset diabetes subjects [Velthuis, 2010; Unger, 2011] Interestingly, analyses of pancreata from subjects diagnosed with diabetes within 1 year suggest that subjects under the age of 14 have higher incidence of insulitis (68%) compared to those between 15 and 39 (39%) [In't Veld, 2014]. This suggests that a more vigorous autoimmune attack occurs in children. As a consequence of this autoimmune attack, autoantibodies against: glutamic acid decarboxylase (GAD), protein tyrosine phosphatase-related islet antigen-2 protein (IA 2), IA 2 β , islet-cell antigen (ICA), zinc transporter 8 (ZnT8) and/or insulin (IAA) are detectable in approximately 85% to 90% of subjects with T1D [Vermeulen, 2011]. But as discussed earlier, these autoantibodies can neither predict absolute disease progression nor be used to monitor therapeutic efficacy.

The net effect of autoimmune destruction of beta cells coupled to little or no regeneration marks a progressive deterioration of glucose homeostasis, culminating in an absolute dependence on exogenous insulin replacement therapy. It is estimated that only 10-20% of beta-cells are still functioning at the time of clinical diagnosis [Knip, 2002]. The rate of progression from normo-glycaemia, through pre-clinical impairment of glucose handling to insulin dependence is variable. Indeed, even 1-5 years after diagnosis, about 50% of T1D subjects show clinically meaningful beta-cell function [Palmer, 2009].

The destruction process of beta cells is not a continuous phenomenon and it has been argued that T1D is a relapsing-remitting disease [Von Herrath, 2007]. Therefore in order to prevent further deterioration of the pancreas it is vital that subjects are treated as close to or prior to diagnosis if possible.

Clinical trials in T1D/NOT1D usually rely on metabolic measurements as endpoints, most commonly C-peptide, HbA1c, mixed meal tolerance test and insulin usage

[[Aronson](#), 2014]. Reliable biomarkers of immune dysfunction and beta cell destruction are not available at the moment and it is hypothesized that analysis of lymphocyte phenotypes and additionally the deep phenotyping of T and B cells in the earliest stages of the autoimmune process in T1D / NOT1D may provide a window on the immune system, which will eventually enable the characterisation of biomarkers and allow an early evaluation of the efficacy of immunomodulatory regimes in future studies.

2.2.2. Lymph node biopsy immunophenotyping

iLN biopsies will be carried out by two related methods in this study: fine-needle aspirate biopsy (referred to as “fine needle aspirate” in this protocol) and core needle biopsy (referred to as “core biopsy” in this protocol).

Immunophenotyping of cells obtained by iLN core biopsies in autoimmune disease was described by van Baarsen [[van Baarsen](#), 2013]. The authors examined the cellular composition of iLNs in HVs compared to subjects with early rheumatoid arthritis (RA) and subjects at risk of developing RA and showed significant changes in B and T cell composition by flow cytometry analysis between groups. This difference was not detected in PBMCs, indicating that studying the composition of immune cells of the iLN has additional value in understanding molecular events in the early phases of an autoimmune disease. Furthermore, biopsy by fine needle aspirate of lymph nodes has been described as a method to immunophenotype cells derived from axillary lymph nodes following skin antigen delivery [[Tatovic](#), 2015].

3. OBJECTIVE(S) AND ENDPOINT(S)

Objectives	Endpoints
Primary	
1)To assess the frequency and phenotype of leukocyte subsets in iLN and peripheral blood in HVs and NOT1D subjects	
 • Absolute number and/or proportion of leukocyte subsets in iLN and peripheral blood
Secondary	
1) To assess the frequency and phenotype of leukocyte subsets in iLN core biopsies and iLN fine needle aspirates in HVs and NOT1D subjects	
 • Absolute number and/or proportion of leukocyte subsets in iLN core biopsies and iLN fine needle aspirates.
2) To assess the safety and tolerability of iLN biopsy as well as expectations and experience of the biopsy procedure.	
 • Number of AEs and SAEs following lymph node biopsy procedure • Descriptive data obtained by a questionnaire on the acceptability of iLN biopsy in research setting.
Exploratory*	
1) To assess suppression activity of T regulatory lymphocytes from the iLN and peripheral blood in HVs and NOT1D subjects	
 • Relative levels of T lymphocyte suppressive activity of cells from iLN and peripheral blood respectively
2) To assess the frequency of cytokine-producing lymphocytes in HVs and NOT1D subjects	
 • Proportion of lymphocyte populations producing pro-inflammatory and/or anti-inflammatory cytokines in iLN and peripheral blood
3) To assess clonal expansion of T and B lymphocyte populations in HVs and NOT1D subjects	
 • Comparison of TCR and BCR usage in lymphocytes in iLN and peripheral blood
4) To assess the gene expression fingerprint of auto-antigen specific lymphocytes in HVs and NOT1D subjects	
 • Gene expression levels of sorted auto antigen stimulated T lymphocyte populations in iLN and peripheral blood

Objectives	Endpoints
5)To assess the phenotype and transcriptomic fingerprint of stromal cells from iLN core biopsy samples in HVs and NOT1D subjects	
 Absolute number and/or proportion of stromal cell subsets and gene expression levels of stromal cell subsets from iLN core biopsy samples

* The Exploratory endpoints are listed in order of priority and the conduct of any experimental assays will be dependent on the material available (i.e. number of cells obtained) from iLN biopsies and peripheral blood.

See Section 8.1 for a description of the intended use of cells from each biopsy procedure.

4. STUDY DESIGN

- A multi-centre, non-drug treatment study to compare differences in immune cells derived from iLN and peripheral blood of NOT1D subjects and HVs.
- After informed consent, each subject will attend a screening visit followed by a study visit for iLN biopsy and peripheral blood collection (Day 1). Follow up phone calls after the study visit will be carried out at approximately 2 to 4 days and 7 to 14 days after the study visit. The total duration of this study will be up to 10 weeks, including the screening period.
- A data look will be carried out after the recruitment of a cohort of up to 5 HVs to determine if the quality and quantity of cells derived from either fine needle aspirate or core biopsy of the inguinal lymph node and from peripheral blood are likely to be sufficient to continue the study to meet its primary objective. Full details on this feasibility analysis will be provided in the SRM and Reporting and Analysis Plan (RAP).
- Following the data look, for the remainder of the study the team will seek to match NOT1D subjects to HVs at a group level according to the number of subjects for each gender and the distribution of age within gender. Full details on group matching will be provided in the SRM.
- An interim analysis will be carried out after the recruitment of 5 evaluable HVs and 5 evaluable NOT1D subjects. The primary purpose of this interim analysis will be to facilitate decision making and study design for a potential follow-up interventional study.

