1. REPORTING & ANALYSIS PLAN SYNOPSIS

Overview	Key Elements of the RAP
Purpose	The purpose of this reporting and analysis plan (RAP) is to describe the planned analyses and outputs for the second interim analysis after the first 5 healthy volunteers (HVs) and 5 NOT1D subjects, the primary purpose of this interim analysis will be to facilitate decision making and study design for a potential follow-up interventional study.
Protocol	
 This RAP is based on the protocol amendment 3 (Dated: 07-Mar-2017) of study OTX203158 (GSK Document No.: 2015N246275_03] and eCRF Version 1.0.
Primary Objective / Endpoint	
 To assess the frequency and phenotype of leukocyte subsets in iLN biopsies and peripheral blood in HVs and NOT1D subjects, measured by: 
 Absolute number and/or proportion of leukocyte subset in iLN biopsies and peripheral blood.
Secondary Objectives / Endpoint	
 To assess the frequency and phenotype of leukocyte subsets in iLN core biopsies and iLN fine needle aspirates in HVs and NOT1D subjects measured by: 
 Absolute number and/or proportion of leukocyte subsets in iLN core biopsies and iLN fine needle aspirates. To assess the safety and tolerability of iLN biopsy as well as expectations and experience of the biopsy procedure. 
 Number of AEs and SAEs following lymph node biopsy procedure. Descriptive data obtained by a questionnaire on the acceptability of iLN biopsy in research setting.
Study Design	
 A non-drug treatment study to compare differences in immune cells derived from iLN and peripheral blood of NOT1D subjects and HVs. Up to 15 evaluable NOT1D subjects and up to 15 evaluable HVs will be enrolled. The first interim analysis will assess the first 5 HVs, so as to determine the quality and quantity of cells. The second interim will assess the first 5 HVs and 5 NOT1D subjects. Following the interim, for the remainder of the study the team will seek to match NOT1D subjects to HVs at a group level according to the number of subjects for each gender and the distribution of age within gender.
Planned Analyses	
 Interim 1, Interim 2, Final
Analysis Populations	
 Safety, Per Protocol, Core Biopsy, Fine Needle Aspirate Biopsy, Biopsy, Blood

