3. PLANNED ANALYSES

3.1. Interim Analyses

3.1.1. Interim Analysis 1

A data look will be carried after the recruitment of a cohort of up to 5 HVs to determine if the quality and quantity of cells derived from either fine needle aspirate or core biopsy of the inguinal lymph node and from peripheral blood are likely to be sufficient to continue the study to meet its primary objective.

The decision rules for the study to continue are:

- Peripheral blood yields $> 1 \times 10^6$ cells, and
- Yield from either iLN biopsy samples $> 1 \times 10^6$ cells.

In addition, the data from the interim analysis will be used to explore the assumptions and feasibility of the primary statistical analysis, and may also be used for pre-programming of outputs for the final analysis.

If the decision is taken to stop the study at the interim, the full safety outputs plus listings of other collected data will be produced.

3.1.2. Interim Analysis 2

An interim analysis will be carried out after the recruitment of 5 evaluable HVs and 5 evaluable NOT1D subjects. The primary purpose of this interim analysis will be to facilitate decision making and study design for a potential follow-up interventional study.

In addition, the interim analysis results would also help to enable prioritization of the exploratory assays and to facilitate the final RAP. Due to uncertainty around variability and precision, the primary analyses described in Section 7 will be performed in order to re-assess the precision of estimates for the comparisons of interest.

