3. PLANNED ANALYSES

3.1. Interim Analyses

3.1.1. Interim Analysis 1

A data look will be carried after the recruitment of a cohort of up to 5 HVs to determine if the quality and quantity of cells derived from either fine needle aspirate or core biopsy of the inguinal lymph node and from peripheral blood are likely to be sufficient to continue the study to meet its primary objective.

The decision rules for the study to continue are:

- Peripheral blood yields $> 1 \times 10^6$ cells, and
- Yield from either iLN biopsy samples $> 1 \times 10^6$ cells.

In addition, the data from the interim analysis will be used to explore the assumptions and feasibility of the primary statistical analysis, and may also be used for pre-programming of outputs for the final analysis.

If the decision is taken to stop the study at the interim, the full safety outputs plus listings of other collected data will be produced.

3.1.2. Interim Analysis 2

An interim analysis will be carried out after the recruitment of 5 evaluable HVs and 5 evaluable NOT1D subjects. The primary purpose of this interim analysis will be to facilitate decision making and study design for a potential follow-up interventional study.

In addition, the interim analysis results would also help to enable prioritization of the exploratory assays and to facilitate the final RAP. Due to uncertainty around variability and precision, the primary analyses described in Section 7 will be performed in order to re-assess the precision of estimates for the comparisons of interest.

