5.4. Examination of Covariates, Other Strata and Subgroups

5.4.1. Covariates and Other Strata

The list of covariates may be used in descriptive summaries and statistical analyses. Additional covariates and other strata of clinical interest may also be considered.

Category	Details
Covariates	Age, Gender, Site

NOTES:

- The effect of Age/Gender will be explored if it was not possible to match all subjects by age and gender.
- The effect of site will be explored

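### The HV-only feasibility cohort stays in the NOT1D v HV comparisons, and no pre-specified analysis checks for an effect of recruitment phase

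*Protocol*

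**What the plan says.** Protocol section 4 plans a first look at HVs only: "A data look will be carried out after the recruitment of a cohort of up to 5 HVs". Its purpose is to judge whether enough cells of adequate quality can be obtained. Section 3.1 of both RAPs makes it a go/no-go step. It introduces two yield thresholds, one for blood and one for biopsy, with "The decision rules for the study to continue are".

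The interim RAP synopsis uses the same people twice. For the first look: "The first interim analysis will assess the first 5 HVs, so as to determine the quality and quantity of cells". For the next: "The second interim will assess the first 5 HVs and 5 NOT1D subjects". The protocol words the second analysis differently: "An interim analysis will be carried out after the recruitment of 5 evaluable HVs and 5 evaluable NOT1D subjects". Section 3.1.2 of both RAPs follows the protocol. Interim 2 is meant to "facilitate decision making and study design for a potential follow-up interventional study".

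On comparability of the groups, protocol section 4 says: "Following the data look, for the remainder of the study the team will seek to match NOT1D subjects to HVs at a group level". The matching factors are gender and age within gender.

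The model (interim and final RAP, section 7.1.2) has group, sample type, their interaction and a random subject effect. Final RAP 5.4.1 lists the covariates "Age, Gender, Site" and leaves others open. Section 5.5 plans no centre adjustment. No section says when NOT1D enrolment opens, includes a term for date or recruitment phase, or sets the data-look HVs aside.

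**The concern.** A study that must pass a yield test on HVs before it continues, and that speaks of matching NOT1D subjects only afterwards, would naturally collect its earliest samples from HVs alone. If laboratory or biopsy results then moved for any reason between that period and the rest of the study, the movement would fall on one group only and would look like a disease difference.

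NOT1D v HV is the primary comparison, and Interim 2 feeds the design of a possible interventional study. What is at stake is bias in those estimates. The study tests no formal hypothesis, so there is no type I error guarantee to break.

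**Working it through.** **The plan's own figures.** None bears on this point. The cap of 15 per group is a feasibility limit (protocol 8.2). The expected precision of within 1% for PBMC estimates (8.2.1) cannot be reproduced, because the simulation inputs are not given.

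**Inputs from the documents.** Up to 5 data-look HVs; 5 v 5 at Interim 2; at most 15 v 15 at the end, possibly fewer (protocol 8.2.3); 95% intervals (8.4.1).

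**Assumptions.** A step shift of δ between-subject SDs separates early from later samples. The documents give no value, so 0.25 to 2 SD is used. There is one value per subject, a pooled t-interval (simpler than the planned GLMM), and no true group difference.

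**Step 1: share of the shift that enters the unadjusted contrast.** Share = (early HVs / all HVs) − (early NOT1D / all NOT1D).

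- Interim 2, no early NOT1D: 5/5 − 0/5 = 100%
- Interim 2, one early NOT1D: 5/5 − 1/5 = 80%
- Interim 2, two early NOT1D: 5/5 − 2/5 = 60%
- Final, 15 v 15, no early NOT1D: 5/15 = 33%
- Final, if recruitment stops at 10 per group: 5/10 = 50%

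**Step 2: can the analysis separate group from phase?** At Interim 2 with no early NOT1D subject, the design matrix with intercept, group and phase has rank 2 of 3, so no phase term can be fitted. With one early NOT1D subject it can be fitted, but the group SE rises from √(2/5) = 0.632 SD to 1.095 SD. At the final analysis the rank is 3 of 3 and the term is estimable.

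**Step 3: how often the 95% interval excludes zero for one parameter with that shift.** Interim 2 uses the noncentral t with 8 df and noncentrality δ/√(2/5). The final analysis uses 20,000 simulated trials with 5 of 15 HVs shifted. No NOT1D subject is early in either.

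| δ (SD) | Interim 2, 5 v 5 | Final, 15 v 15 | Final bias, δ/3 (SD) |
|---|---|---|---|
| 0.25 | 6.4% | 5.3% | 0.083 |
| 0.5 | 10.8% | 7.0% | 0.167 |
| 1.0 | 28.6% | 12.0% | 0.333 |
| 1.5 | 54.9% | 19.1% | 0.500 |
| 2.0 | 79.1% | 26.9% | 0.667 |

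**Step 4: cost of removing it at the final analysis.** Leaving out five HVs gives SE = √(1/10 + 1/15) = 0.408 SD, against √(2/15) = 0.365 SD. The ratio is 1.118. With t quantiles (23 v 28 df) the interval is 1.129 times as wide. A phase term gives the same 0.408 SD, because with no early NOT1D subject the early HVs then inform only the phase effect. Either route returns the exclusion rate to 5% for a step shift.

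**The case against.** A reader might infer that disease group is fully confounded with calendar time, reagent lot and operators' learning curve, and that no analysis can undo it. The documents do not support that.

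- **Order of enrolment.** No section makes NOT1D enrolment wait for the look. The matching sentence says when matching starts, not when NOT1D subjects may enter. Overlap would make the confounding partial.
- **Control set.** Only the interim RAP synopsis fixes the first five HVs as Interim 2 controls. The protocol and section 3.1.2 of both RAPs ask for five evaluable HVs, and the displays use the Safety population, which is not limited to those five.
- **Mechanism.** Lot changes and learning effects are described nowhere. Protocol 4.4.1 calls for an experienced radiologist, and assay procedures sit in the SRM, which is not among the documents. Several gating definitions differ between the two RAPs (Treg from CD25+ to CD25hi, for example). That makes drift plausible without showing it: it may be clearer notation or uniform re-gating.
- **Room in the plan.** Final RAP 5.4.1 and 7.1.1 allow further covariates. The iLN v blood contrast is within subject, so the group-by-sample-type term cancels a shift common to both tissues on the model scale.

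All of this stands and limits the claim. It does not supply a planned check. The covariate clauses commit to nothing on phase, the within-subject contrast does not cancel a biopsy-specific shift, and the NOT1D v HV contrast within each sample type remains exposed.

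A reader might also want Interim 2 confined to precision, or HV and NOT1D biopsies interleaved. The first would take away part of Interim 2's stated purpose on an unproven premise. The second is constrained by the 8-week limit from diagnosis to biopsy, and is probably too late: final RAP 2.1 already reports in the past tense that exploratory objectives 2 to 5 were not evaluated.

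**Conclusion.** The point holds as a potential confounding with recruitment phase that no pre-specified analysis addresses. It is complete at Interim 2 only if the controls are the data-look HVs and no NOT1D subject was biopsied in the early phase. At the final analysis it is partial (33% of any shift at 15 v 15, 50% at 10 v 10) and can be adjusted for.

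The exclusion rates in the working show sensitivity to assumed shifts. They do not predict how many parameters will be affected, since they suppose the same standardised shift in each. Enrolment order, the existence of drift and its size are all unverified. The check is worth adding because it is cheap and protects the primary contrast.

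**What to change.** 1. In final RAP 7.1, pre-specify a sensitivity analysis of each NOT1D v HV contrast that leaves out the data-look HVs or adds a recruitment-phase term. Keep the current model as primary. The two are equivalent for a step shift when no NOT1D subject is early. If some are early, use the phase term, because dropping only the early HVs would leave the early NOT1D subjects unbalanced. Let the phase effect differ by sample type, so that a biopsy-specific shift is covered.
2. State when NOT1D enrolment opened relative to the look, and report biopsy dates by group.
3. Where those dates show little or no overlap, state with the Interim 2 results that group differences cannot be separated from recruitment phase.

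The cost is one more model run per parameter, a date listing and a sentence of interpretation. No extra subjects are needed. At full enrolment the sensitivity analysis has an SE about 12% larger and, with the HVs left out, a 95% interval about 13% wider. The primary analysis keeps its precision.
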